**8.1.2. Follow-up of Adverse Events**

All events will be followed to resolution or stabilization or until 30 days after the patient completes the study. A final assessment of outcome will be made at that time.

**8.1.3. Relationship to the Study Drug**

The relationship of each AE to study drug is to be assessed by the Investigator according to categories in in [Table 3](#).

**Table 3 Criteria for Determination of AE Relationship to Study Drug**

Unrelated	The event is definitely not associated with the study drug. Other conditions including concurrent illness, progression or expression of the disease state, or reaction to a concurrent medication explain the reported AE.
Unlikely	The temporal association, subject history and/or circumstances are such that the study drug is not likely to have had an association with the observed event. Other conditions including concurrent illness, progression or expression of the disease state, or reaction to a concurrent medication, appear to explain the reported AE.
Possibly Related	The event follows a reasonable temporal sequence from study drug but could have been produced by the subject's clinical state or other therapies administered to the subject.
Probably Related	The event follows a reasonable temporal sequence from the study drug abates upon discontinuation of the study drug and cannot be reasonably explained by known characteristics of the subject's clinical state
Definitely Related	The event follows a reasonable temporal sequence from the study drug abates upon discontinuation or cannot be explained by known characteristics of the subject's clinical state.

**8.1.4. Intensity Assessment**

The intensity of each AE is to be assessed by the Investigator according to the CTCAE, version 5.0; please refer [Table 4](#).

**Table 4 CTCAE Severity grade description**

Grade 1	Mild	Asymptomatic or mild symptoms; clinical or diagnostic observations only; intervention not indicated.
Grade 2	Moderate	Minimal, local or non-invasive intervention indicated; limiting age-appropriate instrumental activities of daily living*
Grade 3	Severe	Severe or medically significant but not immediately life-threatening; Hospitalization or prolongation of hospitalization indicated; disabling; limiting self-care activities of daily living**. Note: An experience may be severe but may not be serious, (e.g. severe headache).

Grade 4	Life-Threatening	Life-threatening consequences; urgent intervention indicated.
Grade 5	Fatal	Death related to AE.

Note: A semi-colon indicates 'or' within the description of the grade.
 
*Instrumental activities of daily living refer to preparing meals, shopping for groceries or clothes, using the telephone, managing money, etc.
 
**Self-care activities of daily living refer to bathing, dressing and undressing, feeding self, using the toilet, taking medications and not bedridden.
		

### 8.1.5. Abnormal Laboratory Values

All laboratory results must be filed in the participant's medical record and monitored. The Investigator or designee must review laboratory results in a timely manner demonstrated by signature/date and assignment of clinical significance assessment. Non-clinically-significant laboratory abnormalities, i.e., minor deviations from the normal range, are expected and it is likely that no medical intervention will be required. Abnormal laboratory results should not be considered AEs unless they are associated with a diagnosis.

Any grade laboratory abnormality that is considered to be clinically significant by the Investigator will be recorded on the AE eCRF. An abnormal test result will be considered as an AE if it is not associated with an already reported AE, diagnosis, or pre-existing condition; if there is a change in concomitant medication or intervention is needed, in direct response to a Grade 3 or 4 laboratory result and if investigator considers the laboratory result to be clinically significant

All such laboratory abnormalities should be repeated and reassessed for 'seriousness' by the Investigator or designee as soon as possible. If a result meets the regulatory definition of 'serious', it should be reported as an SAE following regulatory and protocol requirements. Repeat laboratory tests should be performed regularly to monitor patient status.

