#### 1.4.3.3. *Clinical Safety*

Overall, EYP001a was safe and well tolerated over the dose range of 100 mg to 500 mg QD and 200 mg BID but was better tolerated with the QD regimen than with BID dosing. The most common treatment-emergent adverse events (TEAEs) were gastrointestinal (GI) disorders. These TEAEs were transient and were of mild to moderate intensity. Pruritus was reported, mainly in subjects in the 200 mg BID and 150 mg BID groups. No off-target effect was evidenced. There were no clinically significant changes in vital signs or 12-lead electrocardiograms (ECGs). No SAE or SUSAR was reported.

In most cases, ALT and AST values were within the normal range following EYP001a administration in healthy subjects and after single administration in chronically infected HBV subjects. After 4 weeks of administration of EYP001a to chronically infected HBV subjects, 5 subjects had Grade 3 (n=4) or Grade 4 (n=1) ALT/AST increases without signs of liver dysfunction for all other liver tests (total bilirubin, gamma glutamyl transferase [GGT], ALP, international normalized ratio [INR], and albumin). These changes were interpreted as hepatic flares typical of those seen in patients with underlying chronic viral HBV liver disease with clinically not significant slight ALT changes.

Overall EYP001a is considered safe over the dose range of 100 mg to 400 mg QD and 200 mg BID given as capsules. Aforementioned data initially supported the selection of the 400 mg tablet dose for study EYP001-201. Nevertheless, PK and safety/tolerance preliminary findings in ongoing EYP001-202 NASH phase 2a and in the EYP001-107 phase 1 NASH trials with the EYP001a tablet formulation, do not support the use of the 400mg daily single oral EYP001 dose with the tablet formulation. The reduction to 200mg QD (1x200mg tablet) will generate an exposure similar to 400mg QD (2x200mg capsules) dose that was previously tested and well tolerated. EYP001a 200mg tablet QD dose can be assessed safely in CHB subjects over the planned 16 week treatment period.

For more details on effects in humans, please refer to Section 5 of the IB [[IB, 2019](#)].

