#### 4.6. Stopping Rules

Dosing for a patient will be discontinued for any of the following events:

1. One occurrence of an SAE assessed to be definitely, probably or possibly related to dosing with the study drug.
2. One occurrence of a Grade 4 AE (i.e. life-threatening) assessed to be considered “possibly related” or “probably related” to the study drug
3. One occurrence a Grade 3 rash or higher or acute systemic allergic reaction.
4. Confirmation of any of the study drug discontinuation criteria as described in [Section 8.3](#).
5. Occurrence of any condition that, in the opinion of the Investigator, significantly jeopardizes the wellbeing and safety of the patient and is assessed to be probably related to dosing with the study drug.
6. Clinically significant changes in vital signs or ECGs (such as arrhythmias) assessed to be considered “possibly related” or “probably related” to the study drug (i.e., no alternative explanation likely).
7. Clinically significant changes in the safety laboratory tests assessed to be considered “probably related” to the study drug (i.e., no alternative explanation likely).
8. A subject experiences a breakthrough (defined by quantifiable HBV DNA increase of  $\geq 1 \log_{10}$  HBV DNA copies/mL above LLOQ) the subject should return to the study site for a confirmatory measurement within two weeks, and if virologic breakthrough is confirmed, EYP001a or placebo dosing should be stopped and NA treatment should be continued or modified at the investigator’s discretion.

If two or more patients meet study drug stopping criteria #1, or #3 to #8, recruitment and dosing should be suspended or terminated for the remaining patients, pending the outcome of a DSMC review. The DSMC must review all safety data and provide clearance prior to dosing any additional patients.

If one patient meets study drug stopping criteria #2, recruitment and dosing should be suspended or terminated for the remaining patients, pending the outcome of a DSMC review.

If one patient experiences a Grade 5 common terminology criteria for adverse event (CTCAE) toxicity (based on CTCAE, version 5.0), or if more than 2 patients develop a Grade 3 CTCAE toxicity in the same category, the study will be paused, and safety reports

will be submitted to the DSMC for review and clearance prior to dosing any additional patients.

In other situations, re-initiation of study drug may be considered after consultation with the Medical Monitor.

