##### **Safety & Tolerance:**

- **Pruritus:** In an ongoing study EYP001-202, NASH subjects treated during 12 weeks (with EYP001a 100mg BID or 200mg QD or 400mg QD or Placebo tablets) had an overall pruritus frequency of 15/24 (64%) subjects, all mild or moderate episodes, except for three Grade 3. Five pruritus episodes led to early treatment termination. This is in contrast with previous experience in study EYP001-103, in which CHB subjects were treated during 4 weeks with EYP001a capsules, and had mostly mild or moderate pruritus episodes: 1 subject of 7 to 9 (11% to 14%) in each of the EYP001 arms (100 mg, 200 mg and 400 mg QD) but increased to 6 of 9 (67%) subjects treated with 200 mg BID. One subject terminated early because of pruritus.
- **ALT/AST:** In study EYP001-202, two grade 3 cases of isolated transient ALT/AST increases, with no signs of liver impairment, occurred around Day 56 of treatment. No Hy's law cases occurred (no confirmed DILI). The designation by the Primary Investigators (PIs) of the liver enzyme elevations did not consider these as clinically significant, with a variance over time with few outliers, overall not unexpected in the NASH patient population. This compares and is in line with previous phase 1 trials results, where ALT and AST values were within the normal range following EYP001a administration in healthy subjects and in study EYP001-103 after 4 weeks of administration of EYP001a to CHB subjects, 5 subjects had Grade 3 (n=4) or 4 (n=1) ALT/AST increases without signs of liver impairment. The changes were interpreted as hepatic flares or typical of those seen in subjects with underlying chronic viral HBV liver disease.

Taken together, these PK and safety/tolerance preliminary findings in the ongoing NASH and phase 1 trial obtained with the EYP001a tablet formulation do not support the use of the 400mg daily EYP001 dose as a tablet. The reduction to 200mg QD (1x200mg tablet) will generate an exposure similar to previously tested and well tolerated 400mg QD (2x200mg capsules). EYP001a 200mg tablet QD dose can be assessed safely in CHB subjects over the planned 16 week treatment period.

For more details, please refer to IB memorandum dated 16 January 2020 ([IB Memo, 2020](#)).

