14.3.3.2	Summary of Treatment Emergent Adverse Events by SOC and PT	Safety	X	X
14.3.3.3	Summary of Serious Treatment-Emergent Adverse Events by SOC and PT	Safety	X	X
14.3.3.4.1	Summary of Treatment-Emergent Adverse Events by Relationship to Study Drug by SOC and PT	Safety	X	X
14.3.3.4.2	Summary of Treatment-Emergent Adverse Events by Relationship to ETV by SOC and PT	Safety		
14.3.3.4.3	Summary of Treatment-Emergent Adverse Events by Relationship to TD by SOC and PT	Safety		
14.3.3.5	Summary of Treatment-Emergent Adverse Events by SOC, PT and Severity	Safety	X	X
14.3.3.6	Summary of Treatment Emergent Adverse Events Leading to Study Drug Discontinuation by SOC and PT	Safety	X	X
14.3.4	Laboratory Parameters			
14.3.4.1.1	Summary of Hematology & Coagulation	Safety	X	X
14.3.4.1.2	Summary of Hematology & Coagulation Shifts from Baseline	Safety		
14.3.4.2.1	Summary of Serum Chemistry	Safety	X	X

14.3.4.2.2	Summary of Serum Chemistry Shifts from Baseline	Safety		
14.3.4.3.1	Summary of Lipid Metabolic Profile	Safety	X	X
14.3.4.3.2	Summary of Lipid Metabolic Profile Shifts from Baseline (Low, Normal, High)	Safety		
14.3.4.3	Summary of Urinalysis	Safety	X	X
14.3.4.4	Summary of Maximum CTCAE for ALT, AST, BILI and GGT for Post Treatment Assessments	Safety		X
14.3.5	Other Safety			
14.3.5.1	Summary of Vital Signs	Safety	X	X
14.3.5.2.1	Summary of 12-Lead ECG	Safety	X	X
14.3.5.2.2	Summary of 12-Lead ECG Interpretation	Safety	X	X
14.3.5.3	Summary of Pruritus Assessment - 5-D Pruritus Scale	Safety		
14.3.5.4	Summary of Pruritus Assessment - Visual Analogue Scale	Safety	X	X
14.3.5.5	Summary of Liver Fibrosis and Inflammation Assessment	Safety		
14.3.5.6	Analysis of Liver Fibrosis and Inflammation Assessment: Baseline to Week 16	Safety		X
14.3.5.7	Summary of Liver Imaging	Safety	X	X

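### Section 8.1.5 gives laboratory-AE rules that cannot all be applied, so a Grade 3/4 liver flare could go unrecorded as an AE although the one-patient Grade 4 trigger in 4.6 is written on AEs

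*Protocol*

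**What the plan says.** Protocol 8.1.5 contains three statements on when a laboratory result is an adverse event:

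- **A:** "Abnormal laboratory results should not be considered AEs unless they are associated with a diagnosis".
- **B:** "Any grade laboratory abnormality that is considered to be clinically significant by the Investigator will be recorded on the AE eCRF". No diagnosis is required.
- **C:** "An abnormal test result will be considered as an AE if it is not associated with an already reported AE, diagnosis, or pre-existing condition". Further conditions follow, on a change of medication or intervention for a Grade 3 or 4 result and on clinical significance. The connectives do not show whether these are alternatives or must all be met.

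Two neighbouring sections bear on the same question. Section 8.1 allows an abnormal laboratory finding to be an AE. Section 8.1.6 makes a pre-existing condition an AE if it worsens in frequency, severity or character.

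Section 4.6 uses the AE record. Criterion 2 begins "One occurrence of a Grade 4 AE (i.e. life-threatening" and also needs a possible or probable relationship to study drug; one such patient suspends recruitment and dosing. Criteria 1 and 3 to 8 need two or more patients. Separately, the study pauses if "more than 2 patients develop a Grade 3 CTCAE toxicity in the same category".

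On earlier liver flares, Section 1.4.3.3 describes the Grade 3/4 ALT/AST rises in CHB patients as "typical of those seen in patients with underlying chronic viral HBV liver disease with clinically not significant slight ALT changes". Section 5.4 says of the Grade 3 cases in EYP001-202 that the investigators "did not consider these as clinically significant".

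SAP section 18 lists Table 14.3.4.4, "Summary of Maximum CTCAE for ALT, AST, BILI and GGT for Post Treatment Assessments", and marks it for the second DSMC meeting only.

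**The concern.** Every patient in this trial has chronic hepatitis B as a pre-existing condition, and Section 1.5.2 asks for monitoring of liver-related adverse reactions. The rule that decides whether a liver enzyme rise is an AE should therefore give one answer at every site, and it does not. The earlier EYP001a flares were isolated enzyme rises, either put down to the underlying infection or judged not clinically significant. Those are the features on which 8.1.5 is least clear.

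Three things rest on the answer. One is criterion 2, the only numbered stopping criterion that suspends the study on a single patient. Another is the Grade 3 pause, if its toxicities are counted from recorded AEs. The last is the set of TEAE summaries in SAP 13.1, including the count of TEAEs of Grade 3 or higher.

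**Working it through.** The plan gives no figure on this point to reproduce. The check is textual, followed by a calculation of scale.

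**Step 1: apply the rules to two kinds of Grade 3/4 ALT/AST rise.**

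| Case | A | B | C | 8.1 and 8.1.6 |
|---|---|---|---|---|
| Called clinically significant, no diagnosis made | Not an AE | Recorded | An AE, if its other conditions are met and HBV is not regarded as the link | An AE |
| Attributed to underlying HBV, called not clinically significant, no separate diagnosis | Not an AE | Not captured | Not captured | Could be an AE, as a laboratory finding or as worsening of HBV |

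In the first row A contradicts B outright. In the second, which matches the earlier flares, the rise passes none of the three routes in 8.1.5, and only the neighbouring sections could bring it in. Whether it is recorded depends on which section the site follows.

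**Step 2: trace the case to the study-level rules.** Criterion 2 needs an AE. Protocol Table 4 describes Grade 4 only as life-threatening consequences, so it is also unclear whether a Grade 4 laboratory value without symptoms counts. The Grade 3 pause does not say whether a toxicity is a recorded AE or a graded laboratory value. Criterion 4 reads the numeric limits of 8.3 directly from laboratory values. Criterion 7 needs both a clinically significant and a probably related call. Criteria 4 and 7 act on the study only at two patients.

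**Step 3: scale, as illustration.** Inputs:

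- Grade 4 cases: 1 (Sections 1.4.3, 1.4.3.3 and 5.4 agree).
- Grade 3 cases: 3 (Section 1.4.3) or 4 (Sections 1.4.3.3 and 5.4). The totals are four and five, and the documents do not reconcile them.
- Denominator: 61 CHB patients treated with EYP001a across Phase 1 (Section 1.4.3). Assumed range: 48 (sum of the larger n in each EYP001a arm of Protocol Table 1: 7+8+8+8+8+9) to 73 (all EYP001-103 patients, controls included).
- Sample: 37 planned experimental patients. SAP section 15 says enrolment was suspended after about 25 randomisations; at 3:1 that is 0.75 × 25 = 18.75, about 19.

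Formulas, with X binomial(n, p):

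- P(X≥1) = 1 − (1−p)^n
- P(X≥2) = 1 − (1−p)^n − np(1−p)^(n−1)
- P(X≥3) subtracts one further term, for X = 2.

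For Grade 4 with p = 1/61 and n = 37, (60/61)^37 = 0.542, so P(X≥1) = 0.458. The one-case term is 37 × (1/61) × (60/61)^36 = 0.335, so P(X≥2) = 1 − 0.542 − 0.335 = 0.123.

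| Denominator | n | ≥1 Grade 4 | ≥2 Grade 4 | ≥3 Grade 3 (3 or 4 earlier cases) | ≥2 of any Grade 3/4 (5 earlier cases) |
|---|---|---|---|---|---|
| 48 | 37 | 0.54 | 0.18 | 0.41 or 0.61 | 0.91 |
| 61 | 37 | 0.46 | 0.12 | 0.27 or 0.44 | 0.82 |
| 73 | 37 | 0.40 | 0.09 | 0.19 or 0.33 | 0.73 |
| 61 | 19 | 0.27 | 0.04 | 0.06 or 0.125 | 0.47 |

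The last column bounds the backstop. The documents do not print the CTCAE cut-points for ALT and AST, so they do not show which graded rises would also meet the 8.3 limits. If only Grade 4 cases did, criterion 4 would suspend the study with probability about 0.12. If every Grade 3/4 case did, the figure would be about 0.82 (both at denominator 61, n = 37).

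**The case against.** A reader might infer that 8.1.5 would keep such flares out of the AE record. The text does not go that far. A clinically significant call brings a flare in under B, and worsening of hepatitis B brings it in under 8.1.6. Statement A closes a passage about minor deviations from normal and can be read as limited to those, which a Grade 3/4 rise is not. Section 5.7 lists raised hepatic enzymes among observed possibly drug-related TEAEs, so some were recorded as AEs before. Neither 1.4.3.3 nor 5.4 says whether the cited cases were recorded, and 1.4.3.3 does not say who interpreted them. All this stands: the flare could be missed, not would be.

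A reader might also infer from the SAP table list that the first DSMC meeting would see no graded liver toxicity. That is not so. The shell for Listing 16.2.8.2.1 shows the CTCAE grade for ALT, AST, total bilirubin and GGT, and SAP section 19 marks that listing for both meetings. Individual ALT and AST plots and the stopping-rules listing also go to the first meeting. Only the summary table by arm is missing.

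The strongest objection is criterion 4. It needs no AE entry and no clinical-significance call, and it suspends the study at two patients, where the Grade 3 pause needs three. It is a real safeguard, so the decision to pause does not rest on the local judgement alone. It does not replace a trigger that acts on one patient.

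The rates are also weak evidence. They come from 4-week treatment in patients who were mostly untreated beforehand, some also on peg-IFN, whereas this trial enrols NA-suppressed patients for 16 weeks.

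**Conclusion.** The inconsistency within 8.1.5, and between it and 8.1 and 8.1.6, is plain from the text and needs no assumption. The consequence is conditional: a Grade 3/4 ALT/AST flare judged as earlier ones were could be left off the AE eCRF. What is then at risk is the one-patient Grade 4 trigger, possibly the Grade 3 pause, and the TEAE summaries. The DSMC would still have the graded values in the listing, and criteria 4 and 7 remain as partial backstops.

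The gap between about 0.46 for at least one Grade 4 case and about 0.12 for at least two, in 37 patients, shows that a one-patient and a two-patient rule can differ materially. With about 19 experimental patients the figures are 0.27 and 0.04. They assume that the earlier rate carries over, and they count laboratory events; criterion 2 would also need the relationship call. They are not a forecast for suppressed patients.

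**What to change.** Reconcile Protocol 8.1, 8.1.5, 8.1.6 and 4.6 so that a site reading any of them reaches the same answer on whether a laboratory abnormality is an AE. The text should settle how a diagnosis, pre-existing hepatitis B and the clinical-significance call combine. In 4.6, the sponsor should state whether criterion 2 and the Grade 3/Grade 5 pause read recorded AEs, graded laboratory values, or both. That choice is the sponsor's; no clinical rule or threshold is proposed here. The earlier flare count should be made to agree between 1.4.3 and 1.4.3.3/5.4.

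In SAP section 18, mark Table 14.3.4.4 for the first DSMC safety meeting as well, so that liver grades are summarised by arm there.

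The cost is a protocol clarification (the SAP already cites such letters), an eCRF completion note, and one already specified table added to the first package. Depending on the sponsor's choice, more laboratory events may be recorded as AEs.

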### 8.1.6. Pre-Existing Medical Conditions

A pre-existing medical condition is one that is present at the start of the trial. Such conditions should be recorded on the Medical History eCRF. A pre-existing medical condition should be recorded as an AE or SAE only if the frequency, severity, or character of the condition worsens during the trial. When recording such events on an SAE Report Form and/or AE eCRF, it is important to convey the concept that the pre-existing condition has changed by including applicable descriptors.

## 8.2. Serious Adverse Events

### 8.2.1. Definition

An SAE (experience) or reaction is any untoward medical occurrence that at any dose:

- results in death
- is life-threatening

NOTE: The term "life-threatening" in the definition of "serious" refers to an event in which the patient was at risk of death at the time of the event; it does not refer to an event which hypothetically might have caused death if it were more severe.

- requires in-patient hospitalization or prolongation of existing hospitalization

NOTE: inpatient hospital admission refers to an overnight stay in a health care facility

- results in persistent or significant disability/incapacity
- is a congenital anomaly/birth defect
- is an important medical event described as an event that may not result in death, be life-threatening, or require hospitalization but may be considered an SAE when, based upon appropriate medical judgment, it may jeopardize the subject and may require medical or surgical intervention to prevent one of the outcomes listed in the definitions for SAEs. Examples of such medical events include allergic bronchospasm requiring intensive treatment in an emergency room or at home, blood dyscrasias or convulsions that do not result in inpatient hospitalization, or the development of drug dependency or drug abuse.

**Hospitalization:** Treatment within or admission to the following facilities will not meet the hospitalization criteria (however, if any other seriousness criteria as specified above are met, the event will be considered an SAE and reported immediately):

- Hospital visit of <24 hours duration (e.g. patient presented to emergency room, but not admitted to ward)
- Hospitalization of subjects to receive study treatment
- Subjects admitted to a hospice or nursing home for elective non-specific, general care or social reasons
- Hospitalization for prescheduled or elective procedures (such as for pain management, disease staging/restaging procedures or protocol specific procedures).

**Suspected unexpected serious adverse reaction (SUSAR)**, is defined as any AE for which there is a reasonable possibility that the study drug caused the AE of which the specificity or severity is not consistent with those noted in the current protocol and/or IB and meets one of the above criteria for serious. This refers to any AE that has not been previously observed, (e.g. included in the IB), rather than from the perspective of such an event not being anticipated from the pharmacological properties of the product.

**Unexpected Adverse Event** is defined as an adverse reaction, the nature or severity of which is not consistent with the applicable product information (e.g. IB for an unapproved IP).

